3 OBJECTIVES

3.1 Primary Objectives:

- To assess the safety of a single dose of two formulations of an MK-2048 vaginal film which is intended for extended release of antiretroviral drugs.

3.2 Primary Endpoints:

- Grade 2 or higher Adverse Events

3.3 Secondary Objectives:

- Pharmacokinetics: To describe the pharmacokinetics of MK-2048 drug at 0, 3, 5, 7, 10, 14, and 28 days after film insertion
- Acceptability: To describe the acceptability of two formulations of the MK-2048 vaginal film and identify qualities associated with higher or lower degrees of acceptability

3.4 Secondary Endpoint:

- MK-2048 concentrations in plasma, tissue homogenate, CVL, and rectal and vaginal swab eluents, comparing the two film types
- Acceptability: Self-reported assessment of qualities of the experience with the films drawn from existing survey on microbicidal films, and general acceptability ratings drawn from market research methodology

3.5 Exploratory Objectives:

- To compare the effects of two formulations of the MK-2048 vaginal film on the vaginal microbiota and glycome pre and post study product use
- To describe the pharmacokinetics of Eudragit® polymer to ensure that polymer persistence is proportional to drug release.
- To describe the protective effect of MK-2048 film against HIV in an *ex vivo* biopsy challenge model using cervical tissue

3.6 Exploratory Endpoints:

- Vaginal Microenvironment
 - Quantitative vaginal cultures and quantitative PCR for selected microbiota from vaginal swab
 - Nugent score from vaginal swab
 - Levels of anti-viral activity in CVL
 - Levels of glycoproteins and mucins in CVL
 - Levels of biomarkers of innate immunity in CVL
- Eudragit® pharmacokinetics
 - Eudragit® levels in CVL
- Ex vivo challenge: HIV infection of cervical tissue as measured by HIV-1 p24 replication by ELISA and confirmed either by immunohistochemistry or quantitative PCR assessment of integrated provirus in HIV-1 exposed cervical biopsies

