9.2 Sample Size and Accrual

The primary aim of the study is to assess the local and systemic safety of a single dose of two formulations of an MK-2048 vaginal film. The primary endpoint is the proportion of participants who experience a Grade 2 or higher adverse event. The proposed total sample size is N=48 divided into 2 arms (low and high Eudragit® content assigned at a 1:1 ratio). Based on previous studies of vaginal products conducted at the study site, the accrual of 48 eligible subjects with normal reproductive tracts is expected to require the screening of approximately 90 volunteers. Since unevaluable participants will be replaced, it is anticipated that 48 women exposed to study product will be evaluable for the primary endpoint.

The sample size is based on the exact binomial probability of observing Grade 2 or higher adverse events. **Table 4** gives the upper and lower bounds for the 95% exact binomial confidence intervals of the true Grade 2 or higher adverse event rate at all possible numbers of observed events in a group of size 24 or in the full cohort of 48. Note that the results for more than 50% of events in each group are not listed, but by symmetry can be calculated as 1- the listed rate and 95% CI for the number of non-events. If none of the 48 subjects experience Grade 2 or higher adverse events, the 95% exact 2-sided upper confidence bound for the Grade 2 adverse event rate is 7.4%. In a previous study of a single dose of the high Eudragit® content placebo film, 6 grade 2 adverse events were reported in a cohort of 64 women for an event rate of 9.4%. If similar event rates are observed in the proposed study, we will be able to rule out grade 2 or higher adverse event rates greater than 22.6% in the full cohort and 32.4% in each study arm.

TABLE 4: 95% confidence intervals for the true rate at all possible observed Grade 2 or higher adverse event rates

Number of observed events	Rate (95% CI)	Number of observed events	Rate (95% CI)
0/24	0 (0, 14.2%)	0/48	0 (0, 7.4%)
1/24	4.2% (0.1%, 21.1%)	1/48	2.1% (0%, 11.1%)
2/24	8.3% (1.0%, 27.0%)	2/48	4.2% (0.5%, 14.3%)
3/24	12.5% (2.7%, 32.4%)	3/48	6.2% (1.3%, 17.2%)
4/24	16.7% (4.7%, 37.4%)	4/48	8.3% (2.3%, 20.0%)
5/24	20.8% (7.1%, 42.2%)	5/48	10.4% (3.4%, 22.6%)

6/24	25.0% (9.8%, 46.7%)	6/48	12.5% (4.7%, 25.2%)
7/24	29.2% (12.6%, 51.1%)	7/48	14.6% (6.1%, 27.8%)
8/24	33.3% (15.6%, 55.3%)	8/48	16.7% (7.5%, 30.2%)
9/24	37.5% (18.8%, 59.4%)	9/48	18.8% (8.9%, 32.6%)

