9.3.2 Secondary and Exploratory Endpoints

The secondary and exploratory endpoints of this study are as follows:

Secondary: MK-2048 pharmacokinetics

MK-2048 concentrations in plasma, tissue homogenate, and CVL rectal and vaginal swab eluents, comparing the two film formulations sampled at enrollment and post-enrollment time-points through Visit 8

Secondary: Acceptability

Reports of overall acceptability of the film and qualities of the experience with the film will be measured using a self-report survey drawing items from two sources. Overall acceptability is measured using standard language in market research methodology, each using a 5-point agreement scale followed by an open-ended explanation. Assessment of film-specific qualities of the experience is assessed by a 9-item scale drawn from previous research with participant-inserted films. Questions assess perceptions of leaking, vaginal dryness, and sensation of the film inside the vagina during and after insertion.

Exploratory: Vaginal Microenvironment

Given that there is no non-product use arm, participants will serve as their own control. Assessment of baseline microenvironment will take place during the Enrollment visit with the

exception of CVL properties. CVL will be obtained at the Screening visit so that the microenvironment can recover prior to study product administration at the enrollment visit.

Levels of lectin binding and mucins measured in CVL samples

Endogenous and exogenous glycolytic enzymes, formulated microbicide products, and microbial flora interact with mucins and may alter their structure and function. These alterations may be detected with lectins, which are sugar specific binding molecules, and can be bound to reporter molecules (such as horseradish peroxidase) in an ELISA type assay.

Nugent Score

Clinically significant changes in vaginal flora will be evaluated by a change in the Nugent score baseline (Visit 2, pre-exposure) through Visit 7. The Nugent score is graded 1 to 10 as follows:

Normal, 0 to 3

Intermediate, 4 to 6

BV, 7-10

Any shift from normal at baseline to intermediate or BV at Visit 3, 4, 5, 6, 7, or 8 or shift from intermediate or BV to normal at Visit 3, 4, 5, 6, 7, or 8 will be considered a scientifically meaningful change in vaginal microbiota.

Quantitative vaginal cultures and quantitative PCR

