9.7.3 Secondary and Exploratory Endpoint Analysis

Summary statistics of frequencies and percentages will be provided for categorical data. Means and standard deviations or medians and ranges will be provided for continuous data. Methods for the analyses of the secondary endpoints are described below.

Student's t- and Mann-Whitney U tests will be used, where appropriate, to evaluate differences in the following continuous variables between the study arms: MK-2048 concentrations in plasma, rectal and vaginal swab eluents, and genital tissue, levels of glycoproteins and mucins in CVL, levels of cytokines and innate immunity factors, and antiviral activity in CVL. Between group pre- to post-exposure changes in the above endpoints will also be evaluated using Student's t- and Mann-Whitney U tests, where appropriate, while paired Student's t- and Wilcoxon signed-rank tests will be used to evaluate these changes within each study arm. Mixed effects linear regression will be used to evaluate associations between days of exposure to study product and these outcomes.

Nugent score will be categorized as follows: normal (score 0-3), intermediate (score 4-6), and bacterial vaginosis (score 7-10). Differences in the categorized Nugent score pre and post exposure levels will be evaluated using Fisher's exact, while McNemar's tests will be used to evaluate pre- to post-exposure shifts between normal (score 0-3) and abnormal (score 4-10) vaginal microflora within each study arm. Generalized estimating equations will be used to evaluate differences in the marginal post exposure prevalence of bacterial vaginosis between the two film formulations.

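### The exploratory Nugent shift rule puts worsening and improvement under one label, leaves out intermediate-to-BV, and gives two different visit windows

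*Combined protocol and SAP*

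**What the plan says.** Section 9.3.2 (Nugent Score) sets three categories: normal 0 to 3, intermediate 4 to 6, BV 7 to 10. It announces an evaluation of a "change in the Nugent score baseline (Visit 2, pre-exposure) through Visit 7". The rule that follows covers two kinds of move: "Any shift from normal at baseline to intermediate or BV at Visit 3, 4, 5, 6, 7, or 8", and a "shift from intermediate or BV to normal at Visit 3, 4, 5, 6, 7, or 8". Either one "will be considered a scientifically meaningful change in vaginal microbiota".

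The same section introduces the microenvironment endpoints with "Given that there is no non-product use arm, participants will serve as their own control". The matching exploratory objective in Section 3.5 is "To compare the effects of two formulations of the MK-2048 vaginal film on the vaginal microbiota and glycome pre and post study product use".

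For the analysis, Section 9.7.3 plans:
- a Fisher's exact test on the categorized score, before and after exposure;
- a test within each arm: "McNemar's tests will be used to evaluate pre- to post-exposure shifts between normal (score 0-3) and abnormal (score 4-10) vaginal microflora";
- generalized estimating equations (GEE) comparing post-exposure BV prevalence between the two films.

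Table 5 in Section 9.7.4 lists change in vaginal flora by Nugent score, summarized by frequency, percent, median and range. Section 8.3 says that BV without symptoms is not an adverse event. Section 7.4 says that any drug remaining at Visit 7 is taken out during that visit's lavage.

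**The concern.** The rule is the document's only definition of a Nugent change, so it is the natural source for the Table 5 frequency. Read that way, the reported number has three weaknesses.

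- **Direction.** A woman who develops BV and a woman whose abnormal flora becomes normal each add one to the same count. For a vaginal product these are opposite findings.
- **A missing transition.** A woman who is intermediate at enrollment and then reaches BV is not counted unless she also passes through normal, in which case she is counted for the improvement. The group need not be empty: exclusion criterion 4 in Section 5.5 names only symptomatic BV, so it does not bar women with intermediate flora.
- **Window.** One sentence stops at Visit 7; the next includes Visit 8. Visit 8 is a different state. It follows removal of any residual drug, continuous abstinence is required only up to Visit 7 (Section 5.4, criterion 7), and expected menses are screened out for only 14 days after enrollment (Section 5.5, criterion 7).

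One crossing at any of six visits is enough, and there is no untreated arm to show how often that happens without a film. At stake is how readable the microbiota safety description is. The primary endpoint is not affected.

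**Working it through.** The protocol gives no figure for this endpoint (Table 4 concerns adverse events only), so there is no stated value to reproduce.

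**1. What the rule counts.** Three categories allow six changes. The rule flags four: normal to intermediate, normal to BV, intermediate to normal, BV to normal. It leaves out intermediate to BV and BV to intermediate. In points, a rise of 1 (3 to 4) is flagged, while a rise of 6 (4 to 10) is not.

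**2. Whether another analysis counts the missing move.**

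| Analysis | Directions kept apart? | Sees intermediate to BV? |
|---|---|---|
| Shift rule, 9.3.2 | No | No |
| McNemar within arm, 9.7.3 | Yes, across the 3/4 line | No: both states are abnormal (4 to 10) |
| Fisher on categorized score, 9.7.3 | Compares distributions, not individual moves | At group level |
| GEE on BV prevalence, 9.7.3 | Not applicable | At group level, between films only; an equal rise in both arms shows no difference |
| Adverse events, 8.3 | Not applicable | Not if asymptomatic |

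No planned paired analysis within an arm counts intermediate-to-BV progression.

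**3. Illustration: flags with no film effect.** Documented inputs: 48 women, 24 per arm (Section 9.2); visits at days 0, 3, 5, 7, 10, 14 and 28. Assumed inputs: share normal π = 0.6 to 0.8; day-to-day correlation r = 0.80 to 0.99; a stationary normal/abnormal process. Over a gap of g days,

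P(stay normal) = π + (1 − π)r^g and P(stay abnormal) = (1 − π) + πr^g.

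Take π = 0.7 and r = 0.95, with gaps 3, 2, 2, 3, 4, 14:
- normal at every visit, given normal at baseline: 0.957² × 0.971² × 0.944 × 0.846 ≈ 0.690, so 0.310 cross;
- abnormal at every visit, given abnormal at baseline: 0.900² × 0.932² × 0.870 × 0.641 ≈ 0.393, so 0.607 cross;
- flagged: 0.7 × 0.310 + 0.3 × 0.607 = 0.217 + 0.182 = 0.399, and 48 × 0.399 = 19.2 women, about 10.4 for worsening and 8.7 for improvement.

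For comparison, worsening at one visit only (day 7, purely as an example): π(1 − π)(1 − r⁷) = 0.21 × (1 − 0.698) = 0.063, or 3.0 of 48.

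Across the assumed grid the rule flags 4.0 (π = 0.8, r = 0.99) to 39.9 (π = 0.6, r = 0.80) of 48. The single-visit worsening count runs from about 0.5 to 9.1.

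If visits were instead independent with an assumed crossing chance q each, 1 − (1 − q)⁶ gives 26.5%, 46.9% and 62.3% for q = 5%, 10% and 15%. Correlation between visits lowers these.

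**4. Illustration: progression not flagged.** Suppose a fraction f starts intermediate and a fraction h of those reach BV without ever being normal. The unflagged number is 48 × f × h. With f = 0.10 and h = 0.10 this is 0.5; with f = 0.30 and h = 0.40 it is 5.8. Both fractions are assumed.

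**5. If the any-visit result went into McNemar.** Section 9.7.3 does not name the post-exposure visit. Under the model in step 3, the two discordant cells need not be equal when one baseline group is larger: at π = 0.8 and r = 0.80 they are 0.400 and 0.195. The exact two-sided 5% test with n = 24 then rejects 17.7% of the time with no effect. Across the grid the rate runs from about 0% to 17.7% and passes 5% only at r of 0.90 or lower. At a single visit (day 7) it is at most 2.1%.

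**The case against.** The strongest reply is that the rule is only a definition. No Nugent test in Section 9.7.3 is specified on an ever-crossed outcome, and McNemar already separates the two directions across the normal line. BV prevalence is compared by GEE, the categorized score goes to Fisher's exact, and key organisms are followed by quantitative PCR with a 1-log criterion. The films are randomized 1:1, so background fluctuation is balanced in expectation in the comparison that the objective asks for. Much of this stands, and it rules out several stronger readings.

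- A reader might infer that the plan labels natural fluctuation as a film effect. It does not: Section 9.3.2 says meaningful change and attributes nothing to the film. The own-control wording and the word effects in the objective invite that reading of within-arm change, but do not state it.
- A reader might infer that progression to BV is lost from the plan. It is lost from the rule and from McNemar; the Fisher test and the GEE can show it at group level, and only asymptomatic BV is exempt from adverse-event reporting.
- A reader might infer that a high shift rate would say nothing about the film. The contrast between formulations remains valid. What cannot be isolated is an effect common to both films; that follows from having no untreated arm, and rewording the rule would not cure it.

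The reply does not answer three things: the single label for opposite changes, the absence of any paired count of intermediate-to-BV, and the conflicting window. Table 5 still promises a frequency of change, and this rule is the only stated basis for it.

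**Conclusion.** The point holds as a minor correction to an exploratory endpoint. The pooled directions, the omitted transition, McNemar's shared blind spot and the Visit 7/Visit 8 conflict follow from the text alone. That the Table 5 frequency would use this rule is an inference, because no other definition of Nugent change is given.

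The size is not established. The documents give neither a fluctuation rate nor a baseline Nugent distribution, so 4.0 to 39.9 flagged and 0.5 to 5.8 unflagged of 48 are illustrations under assumed inputs. The ranges are too wide to serve as estimates, and the independent-visit percentages should not be read as expected rates. The illustrations support one cautious conclusion: an any-visit count within an arm can be sizeable with no film effect, so it should not carry an inference.

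**What to change.** 1. In Section 9.3.2 and Table 5, define two outcomes: worsening (normal to intermediate or BV, and intermediate to BV) and improvement. Report them separately, by visit and by arm.
2. Use the same window in both sentences of the Nugent paragraph. If Visit 8 is kept, label it as following removal of residual drug and show it apart from Visits 3 to 7.
3. State that any-visit shift counts within an arm are descriptive because there is no untreated arm, and that comparative conclusions rest on the randomized between-arm contrast. Name the post-exposure visit or visits that the McNemar test uses. McNemar is already planned and cannot see intermediate-to-BV, so it does not replace step 1.

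The cost is SAP wording and one more table. Appendix 1 already schedules Gram stains at enrollment and at every follow-up visit, so no new specimen is needed. The small downside is smaller counts in each category.

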9.4 Blinding

All participants will receive a single dose of the MK-2048 vaginal film. They will be blinded to the formulation with respect to Eudragit® content. Evaluators of the study endpoints will also be blinded to the film formulation.

9.5 Emergency Unblinding

The Principal Investigator can proceed with unblinding for safety concerns, without prior consultation of the PSRT. Details of emergency unblinding are specified in an SOP.

9.6 Random Assignment

The randomization scheme will be generated and maintained by a member of the Data Management Center at the study site, and supplied to the Pharmacy. Women will be randomized to one of the two arms at a 1:1 ratio using a permuted block design with random block sizes of 2, 4, and 6. In order to minimize bias in group assignment, participants will be given study identification numbers. A study staff member will allot the identification numbers in sequential order as participants become eligible to enroll in the study. Numbered study film product packages will include sealed envelopes enclosing documentation of the randomized assignment to film formulation. The randomization scheme will be created for a total of 54 participants; the overage will be created to compensate for participant withdrawals or unusable products.

9.7 Data Monitoring and Analysis

9.7.1 Data Monitoring

This clinical trial will be conducted in compliance with the protocol, GCP guidelines, and applicable regulatory requirements. All research charts are maintained in locked files in a locked room. The research staff, under the direction of the primary investigator, will create and maintain electronic databases using REDCap (Research Electronic Data Capture) which is a secure, web-based application designed for clinical trial data collection that is validated for each study protocol. The databases will be backed up every night onto the University of Pittsburgh's server's back-up system. Appropriate firewall and virus scanning software are installed and updated routinely by the university support staff.

This study will utilize electronic data capture. Site staff will enter data as collected directly into a data entry system. Study data management staff will review the electronic data elements for completeness and accuracy. If there are any responses that are incomplete, unclear, or inconsistent with related data elements, the staff person will speak with the clinician in question as soon as possible to resolve the problem. If necessary, the study staff will make the appropriate change in the electronic database which tracks time and date if a change is made.

9.7.2 Primary Endpoint Analysis

The number of adverse events will be summarized by severity, body system, and relationship to study product using frequencies and percent. Individual participants will contribute once to the calculation of event rates. Differences in the prevalence of adverse events between the study arms will be assessed using Fisher's exact test.

9.7.3 Secondary and Exploratory Endpoint Analysis

Summary statistics of frequencies and percentages will be provided for categorical data. Means and standard deviations or medians and ranges will be provided for continuous data. Methods for the analyses of the secondary endpoints are described below.

Student's t- and Mann-Whitney U tests will be used, where appropriate, to evaluate differences in the following continuous variables between the study arms: MK-2048 concentrations in plasma, rectal and vaginal swab eluents, and genital tissue, levels of glycoproteins and mucins in CVL, levels of cytokines and innate immunity factors, and antiviral activity in CVL. Between group pre- to post-exposure changes in the above endpoints will also be evaluated using Student's t- and Mann-Whitney U tests, where appropriate, while paired Student's t- and Wilcoxon signed-rank tests will be used to evaluate these changes within each study arm. Mixed effects linear regression will be used to evaluate associations between days of exposure to study product and these outcomes.

Nugent score will be categorized as follows: normal (score 0-3), intermediate (score 4-6), and bacterial vaginosis (score 7-10). Differences in the categorized Nugent score pre and post exposure levels will be evaluated using Fisher's exact, while McNemar's tests will be used to evaluate pre- to post-exposure shifts between normal (score 0-3) and abnormal (score 4-10) vaginal microflora within each study arm. Generalized estimating equations will be used to evaluate differences in the marginal post exposure prevalence of bacterial vaginosis between the two film formulations.

Prevalence of microorganisms at each visit as assessed through culture and qPCR will be compared between the study arms using Fisher's exact tests, while pre- to post-exposure shifts will be evaluated within each group using McNemar's tests. Differences between the study arms in the quantity of microorganisms at each visit, as well as the change in quantity, will be evaluated using Mann-Whitney U tests. Meaningful changes will be defined by greater than or equal to 1 log changes in dominant members of the microbiota, including *Lactobacillus* species by quantitative PCR (qPCR), *Prevotella* species by qPCR, *Gardnerella vaginalis* (qPCR), *Atopobium vaginae* (qPCR) and *Megasphaera* phylotype I) qPCR). *Candida* species, facultative gram negative rods, staphylococci and streptococci will be evaluated by cultivation based methods. Fisher's exact tests will be used to evaluate differences in these changes between study arms. Mixed effects linear regression (for continuous outcomes) and generalized estimating equations (for binary outcomes) will be used to evaluate associations between days of exposure to study product and these outcomes.

Descriptive statistics will be performed for HIV infection of cervical biopsies as measured by HIV-1 p24 replication for each study arm and the combined cohort. Differences in HIV-1 p24 replication between study arms will be evaluated using Student's t-or Mann-Whitney U test, as appropriate.

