7.4 Visit 3, 4, 5, 6, 7 and 8: Follow-Up Visits

Visit 3, 4, 5, 6, 7 and 8 procedures are outlined in Table 4. The windows around these study visits are as follows:

Visit 3: Day 3 (2-4)

Visit 4: Day 5 (5-6)

Visit 5: Day 7 (7-8)

Visit 6: Day 10 (9-12)

Visit 7: Day 14 (13-16)

Visit 8: Day 28 (24-32)

Two cervical biopsies will be obtained at Visit 5 only. A CVL will be performed at Visits 7 and 8. Residual drug, if present, will be removed during the CVL at Visit 7. The purpose of Visit 8 is to provide a final safety assessment.

Table 3: Follow-up Visit Procedures

VISIT 3, 4, 5, 6, 7, 8 FOLLOW-UP VISITS	
Component	Procedure/Analysis
ADMINISTRATIVE	
 • Collect/Update Contact Information • Visit Questionnaire • Update medical history and concomitant medications • Protocol counseling excluding Visit 8 (including effective birth control, sexual practices restrictions and vaginal product use) • Assess/Document Adverse Events • Schedule Next Study Visit (excluding Visit 8) • Participant Reimbursement
ACCEPTABILITY	
 • Acceptability Questionnaire (Visit 5 ONLY; prior to biopsy)
BLOOD	
 • MK-2048 level
URINE	
 • Pregnancy test (Visit 5 & 8 and as clinically indicated) • Urine dipstick, as clinically indicated
VAGINAL	
 • pH • Wet Mount, prn • Trichomonas (NAAT), as clinically indicated • Gram Stain • Quantitative Vaginal Culture • Quantitative PCR for microbiota • Vaginal swab for MK-2048 level • Vaginal sample for Future Use*
RECTAL	
 • Rectal swab for MK 2048 (Visit 5 ONLY)
CERVICAL	
 • GC/CT (NAAT), as clinically indicated • Cervical biopsies- two adequate (Visit 5 ONLY) • Cervical sample for Future Use*
CVL (Visits 7 and 8 only)	
 • Levels of antiviral activity • • Levels of glycoproteins and mucins • Levels of cytokines & innate immunity factors • MK-2048 level • Eudragit® levels
PHYSICAL EXAM	
 • Physical Exam, as clinically indicated • Vital Signs (BP)

PELVIC EXAM	
 • Bimanual Exam, as clinically indicated • External Genital & Speculum Exam
--------------------	--

* For participants who have consented to the collection of samples for future use and use of left-over samples for future studies.

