9.7.4 Analysis Cohort

The intent-to-treat cohort (ITT) will be defined as those who were randomized. It will be used for analyses of baseline characteristics, protocol deviations and violations, and trial conduct. The evaluable cohort (Eval) is a subset of ITT participants. Evaluable participants will be defined as participants who complete the Screening and Enrollment visits and return for their day 7 visit within the window for a safety assessment. Non-evaluable participants will be replaced.

TABLE 5: Statistical Analysis Plan

Endpoint	Variable	Statistics
Primary	Adverse Events	Frequency, Percent
	MK-2048 concentration	Mean, SD, Median, Range,
Secondary	Acceptability	Frequency, Percent

Exploratory	Persistence of Eudragit® in CVL defined as any concentration above the lower limit of quantification	Mean, SD, Median, Range
	Levels of glycoproteins and mucins, in CVL	Mean, SD, Median, Range
	Antiviral activity in CVL	Mean, SD, Median, Range
	Change in vaginal flora (Nugent score)	Frequency, Percent, Median, Range
	Culture/qPCR results from vaginal organisms - prevalence	Frequency, Percent
	Culture/qPCR results from vaginal organisms - concentration	Mean, SD, Median, Range
	Change in cytokine and innate immunity factors	Mean, SD, Median, Range
	HIV infection of cervical biopsies in ex vivo challenge	Mean, SD, Median, Range

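### The two films' drug levels are compared by significance test only: no film ratio with confidence interval is planned, and the mixed model states no film term, log scale or actual sampling time

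*Combined protocol and SAP*

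**What the plan says.** The secondary endpoint in section 3.4 is MK-2048 concentration in several matrices, "comparing the two film types"; section 9.3.2 repeats the comparison. The matching objective in section 3.3 is only to describe the pharmacokinetics.

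For the analysis, section 9.7.3 states that "Student's t- and Mann-Whitney U tests will be used, where appropriate, to evaluate differences in the following continuous variables between the study arms", and the list begins with "MK-2048 concentrations in plasma, rectal and vaginal swab eluents, and genital tissue". The same section gives the descriptive summaries: "Means and standard deviations or medians and ranges will be provided for continuous data". Table 5 in section 9.7.4 agrees: "MK-2048 concentration Mean, SD, Median, Range". A further sentence adds a time model: "Mixed effects linear regression will be used to evaluate associations between days of exposure to study product and these outcomes".

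Section 7.4 sets the visit windows: days 2-4 for Visit 3, 5-6 for Visit 4, 7-8 for Visit 5, 9-12 for Visit 6, 13-16 for Visit 7 and 24-32 for Visit 8. Tissue and rectal samples are taken at Visit 5 only.

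**The concern.** The trial has two arms because the films differ in dissolution rate (section 2.3). The useful pharmacokinetic result is therefore how much more or less drug one film delivers than the other at each time, and how precisely that is known. A t or rank test with arm summaries does not supply this. A non-significant result would not show similar release, and a significant one would not give the size of the difference. The sample size in section 9.2 rests on adverse-event precision alone, so precision for drug levels was never set out.

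A smaller matter is time. Neither test uses the actual time since insertion. The one method that could, the mixed regression, is not specified well enough to tell whether it does, or whether it contrasts the films at all.

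**Working it through.** **The plan's own figures.** The only precision figures are exact binomial bounds for adverse events in section 9.2. They reproduce: the upper 95% bound is 7.4% for 0/48, 32.4% for 3/24, and 22.66% for 5/48 (printed as 22.6%). No corresponding figure is given for drug levels.

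**What is stated, side by side.** The endpoint is comparative. The between-film method is a test, the summaries are per variable, and the time model relates outcome to days of exposure. None of these names a between-film difference or ratio, or an interval for one. For bacterial vaginosis, by contrast, section 9.7.3 names a regression model expressly for the difference between the two formulations.

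**Inputs.** From the documents: 24 per film (48 at 1:1, section 9.2) and the windows in section 7.4. Assumed, because the documents do not give them: between-woman SD of log concentration 0.5 to 1.5; log-linear decline with half-life 1 to 7 days; visits spread evenly over each window. Section 2.5 reports plasma half-lives of 3 and 2 hours, but these follow ring removal and do not describe a film still in place.

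**Precision of a film ratio.** The factor for the 95% interval is exp(t × σ × √(2/24)), with t = 2.013 on 46 df. At σ = 1.0, √(2/24) = 0.2887, 2.013 × 0.2887 = 0.581 and exp(0.581) = 1.79. An observed ratio of 1.0 would thus have an interval of 0.56 to 1.79. At σ = 0.5 the factor is 1.34; at σ = 1.5 it is 2.39.

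**Cost of ignoring sampling time.** For a window of m calendar days, the SD of the day is √((m² − 1)/12). The added log variance is (ln 2 / half-life × that SD)², and the inflation is 1 + added variance / σ². Example, Visits 6-7 at a half-life of 2 days: 0.3466 × 1.118 = 0.387; squared, 0.150; inflation 1.15 at σ = 1.0.

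| Visit | Days in window | SD of day | Inflation at half-life 1 d | 2 d | 3.5 d | 7 d |
|---|---|---|---|---|---|---|
| 3 | 3 | 0.816 | 1.32 | 1.08 | 1.03 | 1.01 |
| 4, 5 | 2 | 0.500 | 1.12 | 1.03 | 1.01 | 1.00 |
| 6, 7 | 4 | 1.118 | 1.60 | 1.15 | 1.05 | 1.01 |
| 8 | 9 | 2.582 | 4.20 | 1.80 | 1.26 | 1.07 |

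At Visit 5 (Day 7), with half-life 1 to 3 days and σ 0.8 to 1.0, the extra variance runs from 1% to 19%.

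**In terms of power.** For a true 2-fold ratio, a log-scale t test with σ = 1.0 and no timing noise has 65% power. At a half-life of 2 days, timing noise lowers this to 64% at Visits 4-5, 62% at Visit 3, 59% at Visits 6-7 and 42% at Visit 8. Modelling actual time could at best restore 65%.

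**Choice of test.** On log-normal data with the same ratio and σ, simulated power is about 48% for a t test on raw values and 63% for the rank test, against 65% on the log scale.

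**The case against.** Five points can be made for the plan.

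- **Arm summaries are planned.** A reader might infer that the plan gives no estimates at all. That goes too far: means or medians will be reported, and a rough ratio could be formed from them. What is missing is the contrast itself with its interval, and medians with ranges cannot supply the interval.
- **The mixed regression might already do the job.** Days of exposure could be actual days, and nothing rules out a film term. This stands: the model is under-specified, and the documents do not show that it leaves the film out.
- **Visit-by-visit testing of drug levels is an inference.** Section 9.7.3 says each visit only for microorganisms. This stands too, but no pooled or area-type summary is given either, so how visits enter the drug comparison is simply open.
- **The timing figures rest on assumptions.** Decline may be slow, or may not have begun by Day 3, since the films are meant to release over 7 days. Most women may also attend on the target day. If, for illustration, 70% came on Day 10 and 10% on each of Days 9, 11 and 12, the variance of the day would be 0.56 instead of 1.25; at a half-life of 2 days and σ = 1.0 the inflation falls from 15% to about 7%. This stands.
- **The objective is descriptive and no power for drug levels is claimed.** True, but a descriptive comparison needs an estimate with its uncertainty more than it needs a p-value.

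**Conclusion.** The gap is real and modest. The endpoint promises a comparison of the films, and the plan states no ratio or confidence interval to express it. This does not depend on any half-life. With 24 per film the interval will be wide, about a factor of 1.8 either way at an assumed log SD of 1.0, which is itself a reason to report it.

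Unrecorded use of sampling time is the lesser part. A reader might infer that the windows bias the comparison; the documents do not support that, because allocation is randomised and participants and endpoint evaluators are blinded (sections 9.4 and 9.6). The cost is precision. It is small at Day 7, the time that matters most for proof of concept, and larger at Visits 6 to 8 only if decline is fast. At Visit 8 many samples may be unquantifiable (also an assumption), so the large inflation there may have little practical meaning.

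A reader might also infer a large loss of power from the choice of test. That would hold only for a t test on raw skewed values. The plan already allows the rank test, and the log scale gains about two to three percentage points over it. The case for the log-scale model is the estimate that it yields.

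**What to change.** Specify in section 9.7.3 and Table 5:

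- **Plasma and vaginal swab MK-2048:** the planned mixed model, fitted to log concentration after insertion, with film, visit as a factor, film by visit, and actual time since insertion entered as deviation from the nominal day, with its slope allowed to differ by film.
- **Report:** the high/low geometric mean ratio with 95% confidence interval at each visit where most samples are quantifiable, and the percentage quantifiable per film at every visit, including Visit 8.
- **Tissue and rectal levels (Visit 5 only):** the log-scale ratio with 95% confidence interval.
- **Sensitivity:** keep the Mann-Whitney test.

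This needs no new visits or samples. It does require that insertion and sampling dates and times are captured for every woman, which should be confirmed, since the protocol does not say so outright. It also requires a rule for values below the LLOQ, fixed before unblinding. The model carries a few more parameters, and the intervals will be wide.
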